9.2.5 Respiratory Support Escalation

Sites will record the escalation from non-invasive ventilation to invasive ventilation in the EDC within 24 hours of knowledge of the escalation to invasive ventilation including the event, unless the escalation is due to a planned surgical procedure. If the reason for escalation to invasive ventilation met serious adverse event criteria, the site will record the final diagnosis as an SAE on the SAE eCRF. The DSMB will be notified of the escalation within 1-2 business days by the sponsor or designee.

9.2.6 Time Period and Frequency for Event Assessment and Follow-Up

The site investigator will record all SAEs and ESIs with a start date occurring from informed consent through 28 days after the last dose of study drug (last study drug dose includes weaning doses).

All hypotension and SAEs (study-drug related or not) must be followed until resolution. Events that cannot be resolved by 30 days after the safety-monitoring period will have the status of the ongoing event entered in the EDC system at that time.

In cases when the participant has been transferred to another facility or discharged home, researchers may access test, treatment, and outcome information related to the event from the new treating facility and/or contact the participant/guardian.

9.3 Characteristics of an Adverse Event

Each hypotension event, SAE and other clinical ESI will be assessed by the site investigator for the characteristics in the following sections.

9.3.1 Relationship to Study Intervention

The investigator will use the following question when assessing relatedness of an event of hypotension, ESI, or an SAE to study drug and study procedures, where an affirmative answer designates the event is a SAR:

- Is there a reasonable possibility that the drug caused the event?

“Reasonable possibility” means that there is evidence to suggest a causal relationship between the drug and the adverse event.

To assess relationship of an event to study intervention the following guidelines are used:

1. Related (Possible, Probable, Definite)
 - a. The event is known to occur with the study intervention, and/or
 - b. There is a temporal relationship between the intervention and event onset and/or
 - c. The event abates when the intervention is discontinued, and/or
 - d. The event reappears upon a re-challenge with the intervention.
2. Not Related (Unlikely, Not Related)
 - a. There is no temporal relationship between the intervention and event onset, and/or
 - b. An alternate etiology has been established.

9.3.2 Severity of Event

The investigator should use the following definitions when assessing intensity of an event:

1. Mild: Participant is aware of symptoms or has minor findings but tolerates them well, and no or minimal intervention required
2. Moderate: Participant experiences enough symptoms or findings that may warrant intervention
3. Severe: Participant experiences symptoms or findings that significantly affect clinical status and warrant intervention

9.4 Adverse Event Reporting Procedures

All hypotensive events and SAEs, as defined above, based on physical examination, laboratory findings, MAP measurements, or other means, will be reported in the EDC system within 24 hours of first knowledge of the event. The investigator or designated site personnel will record the required information regarding the hypotension, ESI, or SAE on the appropriate eCRF data fields including, relationship assessment to study drug, outcome, and whether the event met serious criteria.

The DSMB will review hypotension and SAEs on a regular basis. In addition, a qualified and experienced clinician not otherwise associated with this protocol will serve as the Safety Medical Monitor. The Safety Medical Monitor will review valid SAEs at the time they are reported. If safety concerns are identified, the medical monitor may request a meeting of the DSMB to review safety data. At a minimum, the medical monitor will comment on the outcomes of the SAE and causal relationship of the SAE to the study drug. If no SAEs prompt review at an earlier time point, the DSMB will review safety events at the regularly scheduled meeting. Additionally, the DSMB will periodically review interim safety analyses (Section 10). The DSMB will convene and make recommendations on continuation of the study based on review of safety reports and halting rules.

9.4.1 *Expectedness*

The expectedness of a drug-related event (hypotension or SAE) will be determined according to the reference documents containing safety information (the package insert and the protocol). Any SAE that is not identified in nature, severity, or specificity in the current study package insert or protocol is considered unexpected. Events that are mentioned in the package insert or investigational plan as occurring with a class of drugs or as anticipated from the pharmacological properties of the drug, but not specifically mentioned as occurring with the particular drug under investigation are considered unexpected. The study PI and/or study-appointed, clinically/medically-responsible individual will determine whether an AE is expected or unexpected.

9.4.2 *Reporting of Safety Events to FDA*

The Sponsor or designee will notify the FDA and all participating investigators in a written IND safety report of an SAR that, based on the opinion of the investigator or sponsor, is serious, is related to study drug, and is unexpected (per the sponsor) as soon as possible, but not later than 15 calendar days after the sponsor has determined the serious, unexpected SAR (SUSAR) qualifies for expedited reporting. ESI will not be reported as SUSARs. The sponsor will identify all safety reports previously filed with the IND concerning a similar SAR, and will analyze the significance of the SAR in light of the previous, similar reports. Follow-up reports will be sent to investigators to inform and update them about an important SAR if it significantly affects the care of the patients or conduct of the study.

The site investigator will be responsible for reporting adverse events and unanticipated problems involving risks to patients to their local IRBs/IECs in accordance with local regulations.

9.4.3 *Reporting of Hypotension*

If a hypotension event meets serious criteria, it will be reported as an SAE.

Hypotension will be defined as any clinically significant low blood pressure event deemed by the treating physician to require intervention with a fluid bolus or the initiation or escalation of inotropic, vasopressor, or systemic steroid therapy with the specific intent to raise blood pressure.

9.4.4 *Reporting of Pregnancy*

As the participants of this clinical trial are neonates, this section is not applicable.

9.5 Halting Rules

9.5.1 *Discontinuation of a Participant Due to Adverse Events*

Participants may be withdrawn from the study at any time. Participants withdrawn from the study due to a hypotensive event, ESI, or SAE must be followed by the investigator until the clinical outcome from the event is determined, or 28 days after the safety-monitoring period, whichever comes first. Any participant who experiences an event may be withdrawn at any time from the study at the discretion of the investigator. The AE(s) resulting in discontinuation should be noted on the appropriate eCRFs, and the participant's progress should be followed until the AE is resolved or considered stable. The medical monitor or project manager must be notified. If the AE may relate to overdose of study treatment, the package insert should be consulted for details of any specific actions to be taken.

9.5.2 *Unscheduled DSMB Review and Study Discontinuation*

An unscheduled DSMB review of safety data will be triggered if:

- ≥ 3 patients in a cohort have treatment discontinued or an infusion stopped due to the same type of event; or
- ≥ 3 patients in a cohort have a SAR.

Enrollment will be suspended during DSMB review, although study activities will proceed on previously enrolled subjects as applicable.

If the study is discontinued, enrolled participants will continue to be followed for safety assessments for 28 days.

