2.3.1.2 Sildenafil

There are several risks associated with administering sildenafil in premature infants, including:

1. A theoretical increased risk of ROP associated with sildenafil has been suggested in a case report in the literature;⁴⁷ however, case-control and cohort studies have not found a significant association between sildenafil exposure and ROP.^{48–50}
2. Sildenafil has vasodilatory properties that can result in mild and transient decreases in blood pressure. See sildenafil package insert for additional information.¹

Adverse events were previously observed in the phase 1 opportunistic pilot study of sildenafil in premature infants (NICHD-2012-SIL0; see Table 2, Section 2.2). Safety data will also be reviewed prior to dose escalation between cohorts. Risks of ROP have been minimized by administering sildenafil during the time when screening for ROP begins (31-32 weeks adjusted age). Treatment of ROP is an exploratory outcome (Section 3.3.1).

2.3.2 *Potential Benefits*

Sildenafil may improve pulmonary mechanics, reduce exposure to mechanical ventilation, and prevent PH. Although these improvements are not proven, improved pulmonary function and decreased risk of PH are potential benefits for participants enrolled in the study who receive sildenafil. Conclusions drawn from this study will benefit infants receiving sildenafil in the future through better understanding of dose response and characterization of the safety profile of sildenafil.

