5.5 Participant Withdrawal or Discontinuation from Study Procedures/Intervention

5.5.1 *Reasons for Participant Withdrawal or Discontinuation from Study Procedures/Intervention*

The participant's parent or guardian may withdraw an infant from participation in the study at any time. Parents or guardians can choose to have infant discontinue study drug and continue to be followed or they can withdraw consent for further participation at any time.

The site investigator may choose to suspend study drug dosing once for up to 48 hours for any reason. If study drug is resumed by the site investigator, the dose and interval of the study drug will be the same as the prior dose. If applicable, subsequent doses will follow the dose escalation or weaning schedule as specified in section 6.1. If study drug is suspended for > 48 hours, the study drug administration will be discontinued and the participant will proceed directly into the safety follow-up period, during which all remaining assessments will be collected. If study drug is suspended for > 48 hours for a documented safety concern, the suspension will not be considered a protocol deviation.

The site investigator will withdraw a participant from receiving further study interventions, including study drug administration, and the participant will enter the 28-day safety-monitoring period if any of the following occur:

- During the course of the study, the participant meets safety-related criteria that would have led to initial exclusion from study participation (i.e., ALT > 150 U/L, AST > 225 U/L, or infant started on vasopressor or inhaled nitric oxide [Section 5.2]).
- Any clinically significant AE (e.g., hypotension) that is deemed by the site investigator to require discontinuation of study drug (see Section 9.5.3 for the definition of hypotension).
- Unmasking of the participant treatment occurs. All unmasking events should be recorded on a protocol deviation form in the EDC system within 24 hours of the unmasking. The decision to unmask will be made in consultation with the medical monitor.

Before discontinuing a participant from the study drug, the site investigator must contact the medical monitor or study PI, except in emergencies. All participants who have study drug suspended will continue to be in the study and complete all remaining study procedures in the safety follow-up period.

5.5.2 Handling of Participant Withdrawals from Study or Participant Discontinuation of Study Intervention

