6.2 Dosage, Preparation and Administration of Study Product

The investigational pharmacist will be unmasked, and will prepare masked study drug. Detailed information will be included in the MOP. The pharmacy at each site will prepare and distribute the study drug in a masked manner and drug will be administered by the bedside nurse.

Intravenous doses of study drug will be administered as infusion over 60 minutes followed by 30 minutes of flush.

Enteral doses will be administered with feedings. The enteral formulation, if used, will be administered enterally either by mouth, orogastric, nasogastric, gastrostomy tube, or other enteral tubes. For enteral administration in infants receiving bolus feedings, mixing and timing of administration may follow the institutional policy. If there is no specific institutional policy, it is recommended that the study drug be mixed in 10 mL of feedings to be given at the end of the feed. If feeds are administered on pump, timing of administration may follow the institutional policy. If there is no specific institutional policy, it is recommended that study drug be mixed in the last 30 minutes of feeding volume.

If the participant experiences signs or symptoms deemed by the investigator to be clinically significant hypotension or study drug-related SAE, the infusion or feeding will be stopped. Continued study drug administration will be decided by the clinical team.

Refer to the MOP for specific details and recommendations for the use of IV and enteral dilutions for small drug volumes.

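### The first trigger for an unscheduled DSMB review counts a stopped infusion but not a stopped enteral dose, so some enteral stops that are later resumed count less than the same IV stops

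*Combined protocol and SAP*

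**What the plan says.** Section 6.2 sets one bedside rule for both routes. If the investigator sees clinically significant hypotension, or an SAE attributed to study drug, "the infusion or feeding will be stopped". It then adds: "Continued study drug administration will be decided by the clinical team". Section 5.5.1 permits a pause: "The site investigator may choose to suspend study drug dosing once for up to 48 hours for any reason". A dose that is stopped and resumed within that limit is a suspension, not a discontinuation.

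Section 9.5.2 has two triggers, each needing at least three patients in a cohort. Trigger 1 counts patients who "have treatment discontinued or an infusion stopped due to the same type of event". Trigger 2 counts patients with a SAR, which under Section 9.3.1 means an event judged to have a reasonable possibility of being caused by the drug. Either trigger suspends enrollment while the DSMB reviews. No other section extends trigger 1 to enteral doses.

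Route is at the investigator's discretion (Section 6.1, Table 3), and Section 5.4.1 discourages placing an IV line only for study drug.

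**The concern.** Section 6.2 names infusion and feeding together, and Section 9.5.2 names only the infusion. Trigger 1 is the one that needs no causality judgement, so it protects against a drug effect being put down to something else. For an enteral dose that is stopped and then resumed, that protection is absent. Two things follow:

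- If the event is also judged not related, the infant counts toward neither trigger.
- If it is judged related, the infant counts toward trigger 2 only. A not-related IV stop of the same kind counts toward trigger 1 only. Three like events can then be spread over the two counts with neither reaching three.

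At stake is whether a rule that suspends enrollment depends on how the dose was given rather than on what happened to the infant.

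**Working it through.** **Step 1. Which stops count.** Reading Sections 5.5.1, 6.2, 9.3.1 and 9.5.2 together:

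| Stop | Judged related | Trigger 1 | Trigger 2 |
|---|---|---|---|
| IV, resumed or not | yes | counts | counts |
| IV, resumed or not | no | counts | – |
| Enteral, then discontinued | yes | counts | counts |
| Enteral, then discontinued | no | counts | – |
| Enteral, resumed | yes | – | counts |
| Enteral, resumed | no | – | – |

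The last two rows are the gap. It is narrowed in two ways. Section 5.5.1 requires withdrawal of an "infant started on vasopressor or inhaled nitric oxide", which turns such a stop into a discontinuation. A stop for an SAE attributed to the drug is already a SAR.

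**Step 2. The plan's own figure.** The protocol gives no operating figure for the triggers. The nearest is in Section 12.2, the chance of at least one hypotension case at a rate of 0.05. 1 − 0.95^30 = 0.785 (stated as 78%) and 1 − 0.95^90 = 0.990 (stated as 99%). Both reproduce.

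**Step 3. Inputs.** From the protocol: n = 40, because the rule counts patients in a cohort, placebo included (Section 4). As stop rates p, the hypotension rates 0.05 (Section 12.2) and 0.10 (lowest in Table 8) are borrowed. Assumed, because the protocol is silent: enteral share of stops e = 0.5 to 0.8, share of enteral stops resumed r = 0.5, share judged not related u = 0.10.

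**Step 4. Formulas.** Per infant, for one type of event:

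- trigger 1 only: A = p(1 − er)u
- trigger 2 only: B = p·er(1 − u)
- both: C = p(1 − er)(1 − u)
- neither: D = p·e·r·u

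As written, P(review) = 1 − P(a + c ≤ 2 and b + c ≤ 2), with counts a, b, c multinomial in 40 infants. With enteral stops added to trigger 1, every stop counts there, so P(review) = 1 − P(Bin(40, p) ≤ 2).

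**Step 5. One case in full.** With p = 0.05 and e = 0.5: A = 0.00375, B = 0.01125, C = 0.03375, D = 0.00125 (sum 0.05). As written: 0.293. With the fix: 1 − (0.95^40 + 40 × 0.05 × 0.95^39 + 780 × 0.05² × 0.95^38) = 0.323. The loss is 3.0 points. Removing only the uncounted infants, without splitting, gives P(Bin(40, 0.05 − 0.00125) ≥ 3) = 0.309. So about 1.4 points come from stops that count nowhere and 1.6 from splitting.

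**Step 6. Results for u = 0.10.**

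| p | e | As written | With fix | Loss (points) | Expected infants counted nowhere (40·D) |
|---|---|---|---|---|---|
| 0.05 | 0.5 | 0.293 | 0.323 | 3.0 | 0.05 |
| 0.05 | 0.8 | 0.281 | 0.323 | 4.2 | 0.08 |
| 0.10 | 0.5 | 0.743 | 0.777 | 3.4 | 0.10 |
| 0.10 | 0.8 | 0.729 | 0.777 | 4.9 | 0.16 |

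At p = 0.20 the loss is under 1 point, because the review is almost certain either way (0.986 to 0.988 against 0.992).

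**Step 7. Sensitivity to u.** With u = 0.25 the loss is about 7 to 10 points at p = 0.05 and 8 to 13 at p = 0.10. With u = 0.50 it is about 11 to 17 and 15 to 25.

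**Simplifications.** One stop rate for all 40 infants, one route per infant, and all stops of one event type. Using hypotension incidence as a stop rate probably overstates p, since the endpoint runs to 28 days after the last dose and not every episode interrupts a dose.

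**The case against.** The strongest reply is that what escapes carries little drug-safety signal. Section 2.3.1.2 already states: "Sildenafil has vasodilatory properties that can result in mild and transient decreases in blood pressure". Section 9.3.1 accepts as grounds for a related judgement that "There is a temporal relationship between the intervention and event onset", or that the event is known to occur with the drug. Most hypotension during a dose should therefore be a SAR and count under trigger 2 by either route. The stops that count nowhere would mainly have an established other cause, need no vasopressor or inhaled nitric oxide, and be followed by resumed dosing. This stands. It is why u = 0.10 is more plausible than 0.50 and why the effect is small. It does not justify the difference by route: the same not-related, resumed event counts if the dose was IV.

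Second, the routes differ physically. An infusion lasts 60 minutes plus a flush, while Section 6.2 recommends, absent local policy and for bolus feeds, that "study drug be mixed in 10 mL of feedings to be given at the end of the feed". Mid-dose enteral stops may be uncommon. The only related phase 1 event was tied to an IV infusion rate (Section 2.2), which may be why infusions are named. That is possible, but the protocol does not say so, and Section 6.2 itself foresees a stopped feeding.

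Third, there are backstops. Hypotension is entered within 24 hours, the DSMB reviews it regularly, the medical monitor may request a meeting (Section 9.4), and an unblinded review precedes each next cohort (Section 10). A reader might infer from the wording that enteral hypotension goes unmonitored, or that no enteral stop can trigger a review. The protocol supports neither: enteral stops count whenever treatment is discontinued or the event is judged related. Two limits remain. Section 9.4 ties the medical monitor's review at the time of reporting to SAEs, and DSMB meeting frequency is left to the charter.

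**Conclusion.** The wording gap is real, and its effect is probably small. As written, a resumed enteral stop misses trigger 1, and misses both triggers if judged not related. Like events can also split between the triggers. Under the inputs assumed above with 10% judged not related, the chance of an unscheduled review falls by about 3 to 5 points at stop rates of 0.05 to 0.10. The figure is illustrative and depends most on how often hypotension stops are judged not related. The larger losses at 50% should not be read as the expected size, since Section 9.3.1 points the other way. The consequence is a review that may come later, not events that go unseen. The DSMB charter and Safety Management Plan were not available and may already settle the reading. This is a low-priority point, worth making because the correction is so cheap.

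**What to change.** In trigger 1 of Section 9.5.2, replace *an infusion stopped* with *an infusion or enteral dose (feeding) stopped*, and use the same words in the DSMB charter. If enteral stops are left out on purpose, one sentence should say so and why.

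Do not add held doses in general. Section 5.5.1 allows a suspension for any reason, so holds unconnected with drug safety could suspend enrollment. If, say, 5% of infants (an assumed rate) had a hold for one type of event, the chance of at least three in 40 is 0.323 from holds alone. Because an enteral dose can be finished before blood pressure falls, the team may still want some holds to count. If so, limit them to a next dose held for hypotension or for an SAE attributed to study drug.

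The cost is a few words in two documents and slightly more unscheduled reviews, each with enrollment suspended while the DSMB meets.

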10 STUDY OVERSIGHT

An independent DSMB will monitor the progress of the study to ensure study participant safety. Responsibilities of the DSMB will include review of accumulated safety data and assessments to ensure the safety of participating study participants and overall integrity of the study, provide recommendations regarding the further conduct of the study and identify any safety issues that may suggest risk to the participants enrolled in the study

or prospective participants. The DSMB will complete an unblinded review of the safety data after 80% of infants within the cohort complete 14 days of treatment. Enrollment to the next cohort will not begin until after the DSMB has completed their review and provided a recommendation that the study proceed.

A DSMB charter will outline the membership, responsibilities, scope of activities, meeting frequency and communication plan between committee, sponsor, DCRI, and study sites.

11 CLINICAL SITE MONITORING

Clinical site monitoring will be conducted to ensure that human participant protection, study procedures, laboratory procedures, study intervention administration, and data collection processes are of high quality and meet sponsor, GCP/ICH, and regulatory guidelines, and that the study is conducted in accordance with the protocol and sponsor standard operating procedures. The IND sponsor, or its designee will conduct site-monitoring visits as detailed in the Clinical Monitoring Plan (CMP).

Most monitoring activities will be performed remotely, while other monitoring will take place at the study sites. Study team staff from the DCRI will conduct monitoring activities and provide reports of the findings and associated action items in accordance with the details described in the CMP. Documentation of monitoring activities and findings will be provided to the site study team.

